We plan to enroll thirty-two patients with HLHS in a two staged enrollment process. In this study, a maximum of 21 patients will receive intramyocardial injection of c-kit⁺ cells and 11 standard of care control patients with no injection. The enrollment of the patients will occur in two staged groups: Group A and Group B. Initially in Group A, 10 consecutive HLHS patients will be enrolled in the c-kit⁺ cell treatment arm to determine feasibility and safety. Six months after the last patient is enrolled in Group A, the DSMB will conduct a review of all Group A patients in order to determine whether the methodology is feasible and safe, including the harvesting, processing, and administering of the c-kit⁺ cells. Thereafter, Group B will enroll a total of 22 HLHS patients which will be randomized, double-blinded to the treatment and standard of care control arms in a 1:1 ratio, respectively, in order to have 11 c-kit⁺ cell-treated patients and 11 control patients. Randomization will occur post-Norwood operation upon receipt of viable tissue sample at University of Miami Clinical Research Cell Manufacturing Program (CRCMP). The rationale underlying this two-staged enrollment is to initially test the feasibility and safety of this methodology of obtaining the c-kit⁺ cells from the right atrial appendage with the Group A patients. The second Group B patients may provide the required numbers to potentially validate the efficacy of the trial. Eventually, a Phase II trial will provide the necessary numbers to provide an accurate assessment of efficacy of the c-kit⁺ cells in HLHS patients.

B.1.2. Sample Size

Twenty-one (21) subjects will be enrolled in the treatment group and eleven (11) in the standard of care control group. The 10 Group A subjects are part of an open-label safety and feasibility analysis. The 22 Group B subjects will be randomized 1:1 to cell treatment and control to detect a difference of 6 RVEF units, given a standard deviation of 4, 89% power and type 1 error of 0.05. Twenty patients are needed with 10% added for possible lost to follow-up.

B.1.3. Dosage and Administration

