All subjects will be cared for according to institutional standard postoperative protocols, which included standard of care post-surgery assessments. Research-related study visits will occur at Day 5 (\pm 3 days), Week 4 (30 days \pm 7 days), Month 6 (180 days \pm 30 days) and Month 12 (365 days \pm 30 days) (see Table 1). Data from standard of care visits can be used for study visits if collected within visit window. If a patient remains hospitalized at the planned visit date, the assessment will be performed as an inpatient.

The following assessments will be collected post-Stage II BDCPA operation (Day 0) visits as part of standard of care:

- a. Physical exam and vital signs (length, weight, head circumference, oxygen saturation, heart rate, respiratory rate, blood pressure, and Modified Ross Score for heart failure classification (see Appendix A))
- b. 12 lead electrocardiogram
- c. Complete TTE (Day 5, Month 6, and Month 12)
- d. Laboratory assessments at 5 days, 6 months, and 12 months:
 1. Clinical chemistry: BUN, creatinine, sodium, potassium, chloride, glucose, calcium, bilirubin (total), total protein, albumin alanine aminotransferase (ALT), aspartate aminotransferase (AST), B-type Natriuretic Peptide (BNP).
 2. Hematology: complete blood count (CBC) with differential and platelet count
- e. 24-hour Telemetry (Day 5)
- f. AE monitoring

The following research-related assessments will be collected post-Stage II BDCPA operation (Day 0):

- a. cMRI scan (Month 6 and Month 12)
- b. ITQOL survey (Month 6 and Month 12)

- c. Biomarker blood collection (Day 5, Month 6, and Month 12) (See MOP for collection and shipping instructions)

Table 1

Test/Procedure	Pre-Norwood	Pre-BDCPA	BDCPA	Post-BDCPA			
		Baseline ¹	Day 0	Day 5 ± 3 days	Week 4 30 days ± 7 days	Month 6 180 days ± 30 days	Month 12 365 days ± 30 days
Informed Consent	X						
Demographics	X						
Medical History		X					
Physical Exam ²	X	X		X	X	X	X
Lab Assessments ³	X	X		X		X	X
Infectious disease testing ⁴	X						
ECG	X	X		X	X	X	X
ITQOL survey		X				X	X
Trans-thoracic Echo (TTE) ⁵		X		X		X	X
MRI ⁵		X				X	X
Cardiac Cath ⁶		X					
Randomization ⁷	X						
Study Product Injection (SPI)			X				
Telemetry				X			
Biomarker blood collection		X		X		X	X
Adverse Event Monitoring		X	X	X	X	X	X

1 – Baseline testing should preferably occur within 30 days of Stage II BDCPA operation (Day 0), however can occur up to 90 days before

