Analyses of bioactivity will be exploratory in nature in order to aid in endpoints, time points, and sample size determination for subsequent larger trials, if appropriate. We will need to look at the totality of data at the end of this study and use best clinical/statistical judgment in developing a larger study design. As an example, we may see improvement in right ventricular function in treated subjects. Given the objective and predictive nature of this endpoint, and in the absence of safety concerns we could make a decision to proceed with a larger study based on this finding alone. Alternatively, if treated subjects exhibited improved tricuspid regurgitation associated with reductions in symptoms or pleural effusion, this constellation of findings might justify proceeding with additional studies. Regarding the primary endpoint for a Phase I/II study, we will need to look at the outcomes from the proposed study as well as the outcomes from similar studies and the evolving consensus of the research community regarding the importance and predictive nature of specific endpoints in this patient population. To account for patient body surface area, RVESV and RVEDV indices are reported.

Bioactivity endpoints are changes from baseline in:

1. RVEF - continuous variable, with improvement indicated by an increase;
2. RVESVI and RVEDVI - continuous, with improvement indicated by a decrease;

3. Tricuspid regurgitation- continuous, with improvement indicated by a decrease

Every effort will be made to obtain all the data from all the enrolled patients in the study. If not, two analytical approaches will be used to account for missing data: multiple imputations and available data. The primary analysis will be based on the available data. Multiple imputations will be used as a sensitivity analysis.

All endpoints will be summarized by treatment group. Summary on continuous variables will include the following descriptive statistics: mean, median, maximum, minimum, standard deviation, and the 95% confidence interval.

For each bioactivity endpoint, the difference (in change from baseline) between treatment arms will be estimated with the 95% confidence interval. The main bioactivity endpoints of interests will be the changes from baseline at 12 months.

Analysis of bioactivity endpoints

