1. Student t-test will be used to assess the difference between the treatments in the change from baseline for continuous outcomes; also, analysis of covariance (ANCOVA) with adjustment for baseline values will be used to assess treatment effect.
2. Wilcoxon rank sum test will be used to assess the difference in treatment effect in the change from baseline for continuous outcomes if normality assumption does not hold.
3. Chi-square test or Fisher's exact test will be used to assess difference between treatments in incidence of categorical outcomes.
4. Logistic regression with baseline covariates will be used to assess treatment effect for categorical outcomes with adjustment for baseline covariates if appropriate.
5. No adjustment will be made for multiple comparisons.

C.6. Determination of Sample Size

A total of twenty-two subjects will be randomized to two groups (eleven control and eleven treated). In our statistical plan we have allowed for a 10% attrition rate, with one subject per group for the bioactivity analysis.

A sample of 20 participants (10 in the treatment group and 10 in the control) provides 89% power with an alpha of 0.05 to detect a 6 unit change in RVEF (with a SD of 4 units) between the stage II operation (baseline) and 12 months later as measured by cMRI

We performed a power analysis based on our pilot study and the PERSEUS trial published in the administration of cardiosphere derived cells in HLHS patients. The sample size for comparing means from two independent samples of a continuous variable is as follows:

$$n_C = \frac{2 * (Z_{1-\alpha/2} + Z_{1-\beta})^2 \sigma^2}{\delta^2}$$

In a 1:1 randomization, $n_A = n_C$, where n_A = number in the active groups and n_C = number in the control group $\delta = \mu_1 - \mu_2$ (difference of 2 means) and σ^2 is common variance. Total sample size is $2n_C$.

$Z_{1-\alpha/2}$ for an α of .05 for a 2-sided test is 1.96, $Z_{1-\beta}$ for power of .89 is 1.21. The primary analysis will consist of one comparison – cKit versus control. We assume that will have a 6 unit change in RVEF with a SD of 4 units based on data from the PERSEUS trial.¹

Analyses of bioactivity will be exploratory in nature in order to aid in selection of dosage, endpoints, time points, and sample size determination for subsequent larger trials.

C.7. Heart Tissue Analysis

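### The 12-month RVEF comparison leaves the Month 6 cMRI and same-visit echo unused when a Month 12 scan is missing, so the planned ANCOVA is biased if that loss follows Month 6 function and differs by arm

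*Combined protocol and SAP*

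**What the plan says.** Section C.5 sets the time point: "The main bioactivity endpoints of interests will be the changes from baseline at 12 months". It offers two approaches to missing data, available data and multiple imputation, and ranks them: "The primary analysis will be based on the available data". Imputation is a sensitivity analysis, and no imputation variables are listed. The methods named for continuous outcomes are a Student t-test on change from baseline and an ANCOVA adjusting for baseline, with a rank-sum test if normality fails. No repeated-measures model appears.

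More is collected than these methods use. Section B.3.3.f schedules "cMRI scan (Month 6 and Month 12" and transthoracic echo at Day 5, Month 6 and Month 12. Table 1 adds both at baseline. The efficacy endpoint in Section 1 names serial echo and MRI at baseline, 6 and 12 months.

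Section C.6 gives the size: "A total of twenty-two subjects will be randomized to two groups (eleven control and eleven treated", with 10% attrition allowed, one infant per group. Section C.2 defines the efficacy set as everyone randomized. Section C.1 promises a SAP before database lock.

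**The concern.** An infant who is alive at Month 12 but has no cMRI then drops out of both named analyses, even with a Month 6 cMRI and a Month 12 echo on file. Missed scans are realistic. Section 1 makes the number of infants who obtain all three MRIs a feasibility endpoint. A new permanent pacemaker is a primary safety event, and section D.4.3 screens every patient for metallic implants before MRI, so a safety event could cost the scan.

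With about 10 infants per arm, each one lost is a tenth of an arm. If the lost infants are those with poor function at Month 6, and more of them, or sicker ones, are lost from one arm, the remaining infants no longer give a fair 12-month contrast. Adjusting for baseline alone does not repair that. The result has a use: C.5 says an improvement in RV function could, on its own and absent safety concerns, justify a larger study.

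**Working it through.** **1. The plan's own figure.** Inputs from C.6: difference 6, SD 4, 10 per arm, alpha 0.05 ("for a 2-sided test is 1.96"). The noncentrality is 6 / (4 × √(2/10)) = 3.35 on 18 df, and the two-sided t-test then has power 88.7%. This matches the stated 89%. The printed formula gives 2 × (1.96 + 1.21)² × 16 / 36 = 8.93 per arm. With 9, 8 or 7 infants per arm scanned at Month 12, t-test power is 84.8%, 79.7% or 73.1%.

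**2. Which planned test is exposed.** The documents give no visit correlations and no missingness model, so what follows rests on assumptions. Take SD 4 at each visit and write the correlations as baseline–6 / baseline–12 / 6–12. Selecting infants on the Month 6 value distorts an analysis to the extent that its outcome still depends on Month 6.

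- ANCOVA: the slope of Month 12 on Month 6 given baseline is (r6,12 − r0,6 × r0,12) / (1 − r0,6²).
- t-test on change: the slope of the 12-month change on the Month 6 value is r6,12 − r0,6.

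| Correlations | ANCOVA slope | t-test slope |
|---|---|---|
| 0.6 / 0.5 / 0.7 | (0.7 − 0.30) / 0.64 = 0.63 | 0.1 |
| 0.7 / 0.5 / 0.8 | (0.8 − 0.35) / 0.51 = 0.88 | 0.1 |
| 0.5 / 0.5 / 0.5 | (0.5 − 0.25) / 0.75 = 0.33 | 0.0 |

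So ANCOVA carries the bias and the t-test on change hardly any, if loss follows the Month 6 level.

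**3. Size.** Simulations with 11 per arm, true difference 6, about 20% missing at Month 12 and 4,000 runs per setting:

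| How Month 12 scans are lost | ANCOVA bias (RVEF units) |
|---|---|
| Same rule in both arms, no Month 6 effect | 0.00 |
| Same rule, 3- or 6-point effect already at Month 6 | −0.18 to −0.54 |
| Low Month 6 RVEF, controls only | −0.33 to −0.43 |
| Low Month 6 RVEF, treated only | +0.36 to +0.44 |
| Low Month 6 RVEF in one arm, stronger dependence | −0.57 (−0.65 with 0.7/0.5/0.8) |

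Most settings fall between 0.2 and 0.6 units, or 0.2/6 = 3% to 0.6/6 = 10% of the target. In the −0.57 setting ANCOVA power was 82%, against 90% for a likelihood that also uses Month 6. The longitudinal estimate was essentially unbiased (within 0.07). The t-test on change was off by at most about 0.16. At 10% missing, with controls-only loss, ANCOVA bias was −0.17 and power 92.0% against 93.8%.

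**4. If loss follows the Month 6 change instead of the level.** The t-test is then exposed as well. With correlations of 0.5 to 0.7 between the two changes, 10% to 30% missing, one rule in both arms and a 3- or 6-point effect already at Month 6, the completers' mean difference is 5.10 to 5.82 for a true 6. Using Month 6 restores 6.0.

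**5. Precision.** With scans missing at random (0.6/0.5/0.7), the SD of the estimate is 1.89 for the t-test, 1.72 for ANCOVA and 1.67 for the longitudinal model: (1.72 − 1.67) / 1.72 = 3% lower than ANCOVA. Across settings the gain over ANCOVA is about 0 to 6%.

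**6. If the unseen Month 12 value drives the loss.** For a true 6, completers give 5.4 to 4.7 and a Month 6 model 5.7 to 4.9. The correction is only partial.

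**The case against.** The strongest reply is that this is an exploratory analysis in a pilot. Section B.1.1 leaves an accurate efficacy assessment to a later Phase II trial, imputation is already planned and could include Month 6 and echo, and a SAP is still to come. That limits the severity. It does not remove the point, because the ranking in C.5 is explicit and nothing ties the imputation to these data.

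A reader might infer several stronger claims that the documents do not support.

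- *That sicker infants missing the last scan biases the comparison by itself.* It does not. With one mechanism in both arms and no effect at Month 6 there is no bias, and with no true effect the rejection rate stays near 5%.
- *That Month 6 and echo data are ignored.* Section 1 names both among the efficacy measurements, and 12 months is the main time point, not the only one. The gap is only that they do not inform a missing Month 12 cMRI.
- *That much information is wasted.* The precision gain is a few percent at most, and nil if correlations are low.
- *That the bias favours one arm.* Its sign depends on which arm loses its sicker infants.

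It is also fair to say that a longitudinal model does not fully answer the most natural examples. An infant too ill for anaesthesia at Month 12 may be missing because of present condition, not observed Month 6 function. Any bias of this size is also small beside a standard error near 1.7.

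**Conclusion.** The point holds in a limited form. As written, the main 12-month comparison uses only infants with both a baseline and a Month 12 cMRI. If loss depends on Month 6 function and differs by arm, including through a treatment effect already present at Month 6, the baseline-adjusted ANCOVA is biased in either direction by roughly 0.2 to 0.6 RVEF units of the 6-unit target. That size assumes about 20% missing and visit correlations of 0.5 to 0.8; it is smaller at the 10% the plan allows. The t-test on change is little affected under those correlations when loss follows the Month 6 level, though not when it follows the Month 6 change. Correlations and missingness are assumptions throughout. This is a cheap improvement worth making before the SAP is finalized, not a flaw that invalidates the trial.

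**What to change.** In C.5 and the SAP, for infants alive with their own heart:

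- Make the RVEF analysis a baseline-adjusted longitudinal model on all cMRI scans (constrained longitudinal analysis or MMRM, unstructured covariance, Kenward-Roger), and report the Month 12 contrast.
- Keep the available-case ANCOVA as a sensitivity analysis.
- Require the planned multiple imputation to include Month 6 cMRI and same-visit echo measures of RV function.
- Add a missing-not-at-random sensitivity analysis, because the model corrects only in part when unobserved Month 12 status drives the loss.

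Death and transplant are outside this remedy and need their own stated rule.

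The cost is SAP text, a little more analysis work and a few extra covariance parameters to estimate from 22 infants, with little or no precision gain if visit correlations are low. No new visit, scan or patient is needed. The simulated likelihood used Month 6 but not the Kenward-Roger adjustment, so the power figures for it are indicative; the SAP author should rerun them with the chosen model.

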Appendix A: Modified Ross Score for Heart Failure Classification

The Modified Ross Score for heart failure classification (25) will be used to assess heart failure during physical exams in the CHILD trial. It will be assessed at baseline and follow-up visits (Day 5, Week 4, Month 6, Month 12)

Score (points)			
	0	1	2
History			
Diaphoresis	Head only	Head and body during exercise	Head and body at rest
Tachypnea	Rare	Several times	Frequent
Physical examination			
Breathing	Normal	Retractions	Dyspnea
Respiratory rate (respirations/min)			
0-1 y	<50	50-60	>60
1-6 y	<35	35-45	>45
7-10 y	<25	25-35	>35
11-14 y	<18	18-28	>28
Heart rate (beats/min)			
0-1 y	<160	160-170	>170
1-6 y	<105	105-115	>115
7-10 y	<90	90-100	>100
11-14 y	<80	80-90	>90
Hepatomegaly (liver edge from right costal margin)	<2 cm	2-3 cm	>3 cm
